9.7.1.7.3 PHARMACOKINETIC/PHARMACODYNAMIC ANALYSIS

The PK/PD relationship between exposure to lemborexant and the efficacy variables including but not limited to sSOL, sSE, and sWASO, and the safety variables including but not limited to morning sleepiness and frequently occurring TEAEs, will be explored graphically. Any emergent PK/PD relationships will be evaluated by population PK/PD modeling. The population PK/PD analysis plan will be described and results will be reported in a separate document.

Population PK and PK/PD analyses will be performed using NONMEM Version 7.2 or later.

9.7.1.7.4 PHARMACOGENOMIC ANALYSES

Not applicable.

9.7.1.8 Safety Analyses

Evaluations of safety will be performed on the relevant Safety Analysis Set and On-Treatment Safety Analysis Set, as appropriate. (revised per Amendment 06)

12-Month Lemborexant Exposure

For visit-based Safety data (ie, laboratory values, vital signs, ECGs, etc), data will be summarized by treatment (LEM5, LEM10) and duration of exposure (1 month, 3 months, 6 months, 9 months, and 12 months). Treatment groups are LEM5 and LEM10, and include both (a) LEM Period 1 subjects on the On-Treatment Safety Analysis Set using the change from Study Baseline, and (b) LEM Period 2 subjects previously receiving PBO on the On-Treatment Safety Analysis Set using the change from Period 2 Baseline. (revised per Amendment 06)

Summaries of exposure and AEs will be summarized for:

- Period 1 data, where treatment groups are PBO, LEM5 and LEM10 on the Safety Analysis Set
- 12-month LEM exposure, where treatment groups are LEM5 and LEM10, and include both (a) LEM Period 1 subjects on the On-Treatment Safety Analysis Set, and (b) LEM Period 2 subjects previously receiving PBO on the On-Treatment Safety Analysis Set. (revised per Amendment 06)

9.7.1.8.1 EXTENT OF EXPOSURE

The extent of exposure (mean daily dose, cumulative dose, duration of exposure) to study drug will be summarized descriptively. Period 1 data with LEM5 or LEM10 will be summarized for: the number (percent) of subjects who completed 1 month (30 or more days), 3 months (90 or more days), and 6 months (180 or more days). Twelve-month (12-month) exposure with LEM5 or LEM10 will be summarized for: the number (percent) of subjects who completed 3 months (90 or more days), 6 months (180 or more days), 9 months (270 days), and 12 months (365 or more days) of dosing. (revised per Amendment 06)

Compliance will be calculated on the basis of number of tablets dispensed, lost and returned. Summaries will provide descriptive summary statistics and number (percentage) of subjects below 80%, between 80% and 120%, and >120%.

9.7.1.8.2 ADVERSE EVENTS

The AE verbatim descriptions (investigator terms from the CRF) will be classified into standardized medical terminology using the MedDRA. Adverse events will be coded to the MedDRA (Version 17.0 or higher) lower level term (LLT) closest to the verbatim term. The linked MedDRA preferred term (PT) and primary system organ class (SOC) are also captured in the database.

A TEAE is defined as an AE that emerges during treatment (including the Run-In Period), having been absent at pretreatment (before the Run-In Period) or

- Reemerges during treatment, having been present at pretreatment (before the Run-In Period) but stopped before treatment, or
- Worsens in severity during treatment relative to the pretreatment state, when the AE is continuous.

Separately, for 12-month exposure analysis, LEM Period 2 subjects previously receiving PBO on the On-Treatment Safety Analysis Set will have a separate definition for TEAE in Period 2, where an AE is defined as (revised per Amendment 06):

- Emerges during Period 2 having been absent prior to Period 2 treatment, or
- Reemerges during treatment, having been present prior to Period 2 treatment but stopped before Period 2 treatment, or
- Worsens in severity during Period 2 treatment relative to the pre Period 2 state, when the AE is continuous.

Only those AEs that are treatment-emergent will be included in summary tables. All AEs, treatment-emergent or otherwise, will be presented in subject data listings. AEs will be classified as TEAEs up to 14 days after the last study treatment.

Adverse events will be summarized using the Safety Analysis Set and, where appropriate, the On-Treatment Safety Analysis Set. The TEAEs will be summarized by treatment group at the start of the TEAE. The incidence of TEAEs will be reported as the number (percentage) of subjects with TEAEs by SOC and PT. A subject will be counted only once within an SOC and PT, even if the subject experienced more than 1 TEAE within a specific SOC and PT. The number (percentage) of subjects with TEAEs during the Run-In Period, and after the Run-In Period will be summarized separately. The number (percentage) of subjects with TEAEs during the Period 1 (Safety Analysis Set) and 12-month LEM exposure (On-Treatment Safety Analysis Set) will also be summarized separately. (revised per Amendment 06)

All the following summaries will be repeated for Period 1 and 12-month LEM exposure. (revised per Amendment 06)

The number (percentage) of subjects with TEAEs will also be summarized by maximum severity (mild, moderate, or severe).

The number (percentage) of subjects with TEAEs will also be summarized by relationship to study drug (Yes [related] and No [not related]). Treatment-related TEAEs include those events considered by the investigator to be related to study treatment.

The number (percentage) of subjects with treatment-emergent SAEs will be summarized by MedDRA SOC and PT for each treatment group. A subject data listing of all SAEs will be provided.

The number (percentage) of subjects with TEAEs leading to discontinuation from study drug will be summarized by MedDRA SOC and PT for each treatment group. A subject data listing of all AEs leading to discontinuation from study drug will be provided.

The number (percentage) of subjects with TEAEs of cataplexy or other events that are characterized according to the customized MedDRA query PT as cataplexy-related events, as well as somnolence and related events, and drug abuse liability will be summarized separately. The number of adjudicated events based on the report of the Adjudication Committee will also reported separately.

Customized MedDRA Queries (CMQ) for AEs that could potentially be considered cataplexy or seizure, somnolence, and related events, and preferred terms related to drug abuse liability, will be summarized. The results of the deliberation of the Adjudication Committee will be reported separately. (revised per Amendment 03)

9.7.1.8.3 LABORATORY VALUES

Clinical laboratory values will be evaluated for each laboratory parameter by subject. Abnormal laboratory values will be identified as those outside (above or below) the normal range. Reference (normal) ranges for laboratory parameters will be included in the CSR for this study. Descriptive summary statistics (eg, mean, SD, median, minimum, maximum for continuous variables, and number and percentage for categorical variables) for the laboratory parameters and changes from Study Baseline will be evaluated by treatment group and visit. This will also be repeated for the 12-month LEM exposure (On-Treatment Safety Analysis Set), summarized by treatment group and duration of exposure. (revised per Amendment 06)

Laboratory test results will be assigned a low, normal, high (LNH) classification according to whether the value was below (L), within (N), or above (H) the laboratory parameter's reference range. Within-treatment comparisons will be based on 3 by 3 tables (shift tables) that, for a particular laboratory test, compare the Study Baseline LNH classification to the LNH classification at Month 6 by treatment group. This will also be repeated for the 12-month LEM exposure (On-Treatment Safety Analysis Set), summarized by treatment group and duration of exposure. (revised per Amendment 06)

Clinical laboratory results post-Study Baseline will be evaluated for markedly abnormal values. A laboratory test will be considered markedly abnormal if the result worsens to meet Eisai grading criteria for laboratory values limit of Grade 2 or higher. If the Grade 2 limit is missing, the Grade 1 limit will be considered. [Appendix 1](#) presents the Eisai grading criteria for laboratory values that were used to identify subjects with markedly abnormal laboratory values. For the incidence of markedly abnormal laboratory values, each subject may be counted once in the laboratory parameter value high and in the laboratory parameter low categories as applicable.

9.7.1.8.4 VITAL SIGNS AND WEIGHT

Descriptive statistics for vital signs parameters (ie, diastolic and systolic BP, pulse, respiration rate, temperature) and weight, and changes from Study Baseline will be presented by visit and treatment group.

Vital sign values will be listed. Clinically notable vital sign values will be identified on the listings as those above (H) or below (L) a clinically notable range. Categorical analyses of subjects (number and percent) who fall outside the below clinically notable vital sign ranges will also be presented for change from Study Baseline (Safety Analysis Set), by treatment group and by time point. This will also be repeated for the 12-month LEM exposure (On-Treatment Safety Analysis Set), summarized by treatment group and duration of exposure. (revised per Amendment 06)

Variable	Criterion Value ^a	Change Relative to Study Baseline ^a	Clinically Notable Range
Heart rate	>120 bpm	Increase of 15 bpm	H
	<50 bpm	Decrease of \geq 15 bpm	L
Systolic BP	>180 mmHg	Increase of \geq 20 mmHg	H
	<90 mmHg	Decrease of \geq 20 mmHg	L
Diastolic BP	>105 mmHg	Increase of \geq 15 mmHg	H
	<50 mmHg	Decrease of \geq 15 mmHg	L

BP = blood pressure, H = high, L = low

^a. Clinically notable means that a value must meet the criterion value and must attain the specified magnitude of change relative to Study Baseline.

9.7.1.8.5 ELECTROCARDIOGRAMS

Descriptive statistics for ECG parameters and changes from Study Baseline (Safety Analysis Set) will be presented by treatment group and visit. This will also be repeated for the 12-month LEM exposure (On-Treatment Safety Analysis Set), summarized by treatment group and duration of exposure. (revised per Amendment 06)

Shift tables will present changes from Study Baseline in ECG interpretation (categorized as normal and abnormal) by time point. (revised per Amendment 03)

For each subject, the maximum observed QTcF, the corrected QT interval calculated using Bazett's formula (QTcB), and the maximum prolongation from Study Baseline in QTcF will be compiled. Categorical analyses of subjects (number and percent) with maximum observed QTcF values >450 ms, >480 ms, and >500 ms and maximum prolongations (from Study Baseline) in QTcF >30 ms and >60 ms will be presented by treatment group and by time point. Categorical analyses of subjects (number and percent) with maximum observed PR values >220 ms, and QRS values >120 ms will be presented by treatment group and by time point. This will also be repeated for the 12-month LEM exposure (On-Treatment Safety

Analysis Set), summarized by treatment group and duration of exposure. (revised per Amendment 06)

9.7.1.8.6 OTHER SAFETY ANALYSES

The results of eC-SSRS assessments will be listed for each subject. The incidence of suicidal ideation or suicidal behavior will be summarized by treatment group as appropriate. Urine drug test results and pregnancy test results will also be listed.

Withdrawal symptoms will be assessed using the T-BWSQ. The mean score will be summarized by treatment group, and number (percentage) of subjects with a score ≥ 3 will be summarized.

9.7.1.9 Other Analyses

Secondary and exploratory endpoints may be additionally presented graphically or analyzed by modeling methods if warranted.

9.7.2 Determination of Sample Size

The sample size was estimated for the comparison of LEM10 and LEM5 with PBO, with respect to the mean change from Study Baseline at the end of Month 6 of the mean sSOL, the mean sSE and mean sWASO. This estimate was based on sequential gate-keeping procedure at the 0.05 α -level as described above. There is sufficient power for both the primary endpoint (sSOL) and key secondary endpoints (sSE and sWASO).

On the basis of the dose finding study E2006-G000-201 (Study 201) for the lemborexant total summaries at Days 8 to 15, the standard deviation of change from Study Baseline for sSOL is assumed to be 33 minutes, for sSE is assumed to be 12% and for sWASO is assumed to be 43 minutes. The LS mean treatment differences at Days 8 to 15 from Study 201 were as follows: for sSE 9.5% for LEM10 and 5.5%, for LEM5; for sWASO -26.6 minutes for LEM10, and -11.3 minutes for LEM5. As a result of the non-normal distribution of sSOL, the LS mean treatment difference is not available (geometric mean ratios were used). Therefore, estimating treatment difference using medians at Days 8 to 15 from Study 201, leads to a median treatment difference of approximately -6.8 minutes for LEM10. For LEM5, a median treatment difference is approximately -13.2 minutes.

To detect a treatment difference in sSOL of at least -8.7 minutes, a sample size of 300 per treatment group at 5% (2-sided) level of significance has >90% power for comparing a dose of lemborexant with PBO.

To detect a treatment difference in sSE of at least 5.5%, a sample size of 300 per treatment group at 5% (2-sided) level of significance has >99% power for comparing a dose of lemborexant with PBO.

For sWASO, total 900 subjects (300 per treatment group) will give 90% power to detect a difference of -11.4 minutes for LEM5 and LEM10 compared to PBO (Table 4). The study is adequately powered to show the statistically significant difference from PBO for LEM10 as well as for LEM5.

Table 4 Sample Size Calculations for Study E2006-G000-303

Alpha=0.05	Difference between Active and Placebo CFB (min)	Power = 80%		Power =90%	
		Sample size per group	Overall group sample size	Sample size per group	Overall group sample size
sSOL (SD=33)	-6.8	371	1113	496	1488
	-7.6	300	900	398	1194
	-8	269	807	359	1077
	-8.7	229	687	300	900
	-9	213	639	284	852
	-10	172	516	230	690
	-11	143	429	191	573
sWASO (SD=43)	-9	360	1080	481	1443
	-9.9	300	900	398	1194
	-10	292	876	390	1170
	-11	241	723	323	969
	-11.4	225	675	300	900
	-12	203	609	271	813

CFB = change from baseline, sSOL = subjective sleep onset latency, sWASO = subjective wake after sleep onset.

The study also has adequate power for the secondary analysis of responders. A sleep onset responder is defined as follows: sSOL at Study Baseline is ≥ 30 minutes and mean sSOL at 6 months is ≤ 20 minutes, and a sleep maintenance responder is defined as follows: sWASO at Study Baseline is ≥ 60 minutes and mean sWASO at 6 months is ≤ 60 minutes and shows a reduction of >10 minutes compared to Study Baseline. A total of 900 subjects gives $>99\%$ power to detect a treatment difference in sleep onset responder rates of 16% and sleep maintenance responder rates of 24.4%.

The above sample size also meets regulatory safety requirements. Even with early discontinuation rates as high as 50% at Month 6 (ie, 150 subjects remaining) and 60% by Month 12 (ie, 120 subjects remaining in each treatment group), the requirement for 100 subjects in each of the elderly and non-elderly age-groups to complete 12-months of treatment on 5 or 10 mg lemborexant will be met. In addition, 420 total subjects would have completed 6 months of treatment of 5 mg or 10 mg lemborexant.

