9.7.1.6 Efficacy Analyses

Where Sleep Diary endpoints are described, the time points refer to the mean of the final 7 nights before the visit unless otherwise stated.

Subjects who discontinue the treatment prematurely will be encouraged to continue to complete the assessments at the protocol defined times (retrieved drop out) until the scheduled time of termination. When available, these data will be used for efficacy analyses. If there are a substantial proportion of early withdrawals, a sensitivity analysis of the primary endpoint will be conducted.

Definitions of Baseline

For the analyses of PBO-controlled endpoints (ie, Day 1 to Month 6), “Study Baseline” is defined as the data captured during the Run-In Period (or during the Baseline Period). For the analyses of data that are not placebo-controlled (ie, Month 7 to Month 12), data from Month 6 visit will be used as the “Period 2 Baseline”. (revised per Amendment 06)

For other endpoints, baseline data are captured during the Run-In and Baseline Period. Details will be specified in the SAP.

12-Month Lemborexant Exposure

Twelve-month (12-month) lemborexant exposure summaries will be summarized by treatment (LEM5, LEM10) and duration of exposure (1 month [30 days] where appropriate, 3 months [90 days], 6 months [180 days], 9 months [270 days] and 12 months [365 days]). Treatment groups are LEM5 and LEM10, and include both (a) LEM Period 1 subjects on the

On-Treatment Full Analysis Set using the change from Study Baseline and (b) LEM Period 2 subjects previously receiving PBO on the On-Treatment Full Analysis Set using the change from Period 2 Baseline. (revised per Amendment 06)

Control of Type 1 Error

A sequential gate-keeping procedure including sSOL (primary endpoint), sSE and sWASO (key secondary endpoints) at Month 6 will control for type 1 error. In order to move from 1 step to the next (steps a to f; below) the outcome must be significant at 0.05 (2-sided).

- a. Change from Study Baseline at Month 6 in sSOL, LEM10 compared to PBO
- b. Change from Study Baseline at Month 6 in sSOL, LEM5 compared to PBO
- c. Change from Study Baseline at Month 6 in sSE, LEM10 compared to PBO
- d. Change from Study Baseline at Month 6 in sSE, LEM5 compared to PBO
- e. Change from Study Baseline at Month 6 in sWASO, LEM10 compared to PBO
- f. Change from Study Baseline at Month 6 in sWASO, LEM5 compared to PBO

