2 DETERMINATION OF SAMPLE SIZE

The sample size was estimated for the comparison of LEM10 and LEM5 with PBO, with respect to the mean change from Study Baseline at the end of Month 6 of the mean sSOL, the mean sSE and mean sWASO. This estimate was based on a sequential gate-keeping procedure at the 0.05 α -level in Section 3.3.3. There was sufficient power for both the primary endpoint (sSOL) and key secondary endpoints (sSE and sWASO).

On the basis of the dose-finding study E2006-G000-201 (Study 201), across various lemborexant doses (1 to 25 mg) at Days 8 to 15, the standard deviation of change from Study Baseline for sSOL was assumed to be 33 minutes; for sSE was assumed to be 12%; and for sWASO was assumed to be 43 minutes. The LS mean treatment differences at Days 8 to 15 from Study 201 were as follows: for sSE 9.5% for LEM10 and 5.5%, for LEM5; for sWASO -26.6 minutes for LEM10, and -11.3 minutes for LEM5. As a result of the non-normal distribution of sSOL, the LS mean treatment difference is not available (geometric mean ratios were used). Therefore, estimating treatment difference using medians at Days 8 to 15 from Study 201, leads to a median treatment difference of approximately -6.8 minutes for LEM10. For LEM5, a median treatment difference was approximately -13.2 minutes.

To detect a treatment difference in sSOL of at least -8.7 minutes, a sample size of 300 per treatment group at 5% (2-sided) level of significance had >90% power for comparing a dose of lemborexant with PBO.

To detect a treatment difference in sSE of at least 5.5%, a sample size of 300 per treatment group at 5% (2-sided) level of significance had >99% power for comparing a dose of lemborexant with PBO.

For sWASO, a total of 900 subjects (300 per treatment group) gave 90% power to detect a difference of -11.4 minutes for LEM5 and LEM10 compared to PBO (Table 2). The study was adequately powered to show the statistically significant difference from PBO for LEM10 as well as for LEM5.

Table 2 Sample Size Calculations for Study E2006-G000-303

Alpha=0.05	Difference between Active and Placebo CfB (min)	Power = 80%		Power = 90%	
		Sample size per group	Overall 3 group sample size	Sample size per group	Overall 3 group sample size
sSOL (SD=33)	-6.8	371	1113	496	1488
	-7.6	300	900	398	1194
	-8	269	807	359	1077
	-8.7	229	687	300	900
	-9	213	639	284	852
	-10	172	516	230	690
	-11	143	429	191	573
sWASO (SD=43)	-9	360	1080	481	1443
	-9.9	300	900	398	1194
	-10	292	876	390	1170

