3.3.3 Multiple Comparisons/Multiplicity

A sequential gate-keeping procedure will be used for primary endpoint and secondary endpoint comparisons to control for the overall type 1 error at the 0.05 significance level. The first endpoint comparison will be tested at the 0.05 significance level. If the testing is

found to be statistical significant, then proceed to the next endpoint testing at significance level of 0.05, otherwise stop testing.

The primary endpoints will be tested in the following order:

- Change from Study Baseline at Month 6 in sSOL, LEM10 compared to PBO
- Change from Study Baseline at Month 6 in sSOL, LEM5 compared to PBO

The key secondary endpoints will only be tested if both primary analyses are statistically significant at the 0.05 level. The key secondary endpoints will be tested in the following order:

- Change from Study Baseline at Month 6 in sSE, LEM10 compared to PBO
- Change from Study Baseline at Month 6 in sSE, LEM5 compared to PBO
- Change from Study Baseline at Month 6 in sWASO, LEM10 compared to PBO
- Change from Study Baseline at Month 6 in sWASO, LEM5 compared to PBO

No multiplicity testing will be performed for other secondary or exploratory endpoints.

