3.4.1 Primary Efficacy Analyses

The primary efficacy endpoint is the change from Study Baseline of sSOL at Month 6 of LEM10 and LEM5 compared to PBO.

Null Hypothesis: No difference exists in the mean change from Study Baseline to Month 6 of treatment with LEM10 (or LEM5) as compared with PBO.

Alternative Hypothesis: For sSOL, a difference exists in the mean change from Study Baseline to Month 6 for LEM10 (or LEM5) as compared with PBO.

The sSOL change from Study Baseline to Month 6 will be analyzed using the mixed effect model repeated measurement (MMRM) analysis on the FAS. The model will be adjusted for the corresponding Study Baseline value, region (North America, Europe and New Zealand, Asia), age group (<65 years old, ≥65 years old), treatment, time (1st 7 nights, Month 1, Month 2, Month 3, Month 4, Month 5 and Month 6) and the interaction of treatment by time. Since the sSOL is known to be non-normally distributed, a log-transformation will be used in the analysis.

The unstructured covariance matrix (UN) will be used in the analysis. In the case of non-convergence of UN, the toeplitz covariance matrix (TOEP) will be used. In the case of non-convergence with TOEP, the autoregressive covariance matrix [AR (1)] will be used in the model.

Before the implementation of the MMRM model, the missing values will be imputed using a pattern mixture model utilizing multiple imputation (MI) assuming the missing values are missing not at random (MNAR) utilizing the complete case missing value pattern (CCMV - subjects who completed all primary efficacy assessments without missing values). The missing values for a given visit will be imputed using all available values including the retrieved measurement from the post-discontinuation data.

The treatment comparison will be performed using contrasts. The p-value, least square (LS) means and the 95% confidence interval (CI) for the treatment difference will also be provided.

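### The sufficient-power claim for sSOL does not hold for LEM10, the first test in the sequence: power is about 71% at the plan's own estimate, and sequence power is not stated

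*Protocol*

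**What the plan says.** Protocol 9.7.2 opens with a general claim: "There is sufficient power for both the primary endpoint (sSOL) and key secondary endpoints (sSE and sWASO". The Synopsis (Sample Size Rationale) carries the same sentence, and SAP 2 has it in the past tense: "There was sufficient power for both the primary endpoint (sSOL) and key secondary endpoints (sSE and sWASO".

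The inputs come from Study 201, Days 8 to 15. The SD of change in sSOL is 33 minutes. There was no mean difference to plan on: "As a result of the non-normal distribution of sSOL, the LS mean treatment difference is not available (geometric mean ratios were used". Medians were used instead, and this "leads to a median treatment difference of approximately -6.8 minutes for LEM10"; the LEM5 figure is about -13.2. The power sentence then uses a third value: "To detect a treatment difference in sSOL of at least -8.7 minutes, a sample size of 300 per treatment group", with power given as above 90%. Stand-alone power is given as above 99% for sSE (5.5%) and 90% for sWASO (-11.4 minutes).

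Sample size is said to rest on the sequential testing procedure. Protocol 9.7.1.6 lists six ordered tests, starting with LEM10 on sSOL, and says: "In order to move from 1 step to the next (steps a to f; below) the outcome must be significant". SAP 3.3.3 adds: "The key secondary endpoints will only be tested if both primary analyses are statistically significant at the 0.05 level".

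On the analysis scale, SAP 3.4.1 says: "Since the sSOL is known to be non-normally distributed, a log-transformation will be used in the analysis".

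**The concern.** The sSOL power sentence answers a different question from the one the design poses. The value -8.7 lies between the two dose estimates and is the difference that Table 4 pairs with 300 per group at 90% power. The other two endpoints are treated differently: sSE is powered at the smaller dose estimate (5.5%, LEM5), and sWASO at a value within 0.1 minute of it (-11.4 against -11.3). Only sSOL is powered at a difference clearly larger than its smaller dose estimate.

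That smaller estimate belongs to LEM10, which is tested first. If that test fails, no later confirmatory claim is possible, including LEM5 on sSOL, which has the larger estimated effect. The sSE and sWASO figures ignore the chance that those tests are never reached. A reader of the Synopsis, which has no Table 4, would conclude that the primary comparison has at least 90% power for either dose.

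**Working it through.** **Inputs.** Two-sided 5% level and 300 per group (Protocol 9.7.2). SDs of change: 33 minutes (sSOL), 12% (sSE), 43 minutes (sWASO). Estimates for LEM10: -6.8, 9.5%, -26.6. Estimates for LEM5: -13.2, 5.5%, -11.3.

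**Method.** Two-sample comparison of means. The standard error is SD × √(2/n), and power ≈ Φ(|difference|/SE − 1.96). The noncentral t gives the exact version.

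**Reproducing the plan.** For sSOL, SE = 33 × √(2/300) = 2.694.
- At -8.7: 8.7/2.694 = 3.229, and Φ(1.269) = 89.8% (noncentral t 89.7%). This is the plan's 90%, though strictly just under the stated figure.
- Sample size at -6.8 by noncentral t: 371 per group for 80% and 496 for 90%, exactly as Table 4 prints. Every other row of Table 4 also reproduces to within a few subjects per group.
- sSE at 5.5%: SE = 0.980, ratio 5.613, power 99.99%. sWASO at -11.4: SE = 3.511, ratio 3.247, power 90.0%.

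So this is the plan's own method.

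**The same method at the plan's sSOL estimates.**

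| Comparison | Difference | Difference/SE | Power (noncentral t) |
|---|---|---|---|
| LEM10 | -6.8 | 2.524 | 71.2% |
| Value in the power sentence | -8.7 | 3.229 | 89.7% |
| LEM5 | -13.2 | 4.899 | 99.8% |

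With 300 per group, the difference detectable with 80% power is 7.56 minutes, and with 90% power 8.75 minutes. The LEM10 estimate is below both.

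**Power through the sequence, at the plan's estimates.** Stand-alone power is 71.2% for step a, 99.8% for b, above 99.9% for c, d and e, and 89.5% for f.
- Steps a to e: about 71%. By the normal approximation the failure probabilities of steps a to e sum to 0.2865 + 0.0016 + 0.0001 = 0.2882. Whatever the correlations, passing a to e therefore lies between 71.2% and the 71.4% for step a alone.
- All six: simulation with a shared placebo arm gives 63.7, 64.5 and 65.5% for assumed endpoint correlations of 0, 0.25 and 0.5, and about 67% at 0.8. Under any dependence the lower bound is 60.8%.

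**Power through the sequence, if both doses had the stated detectable differences (-8.7, 5.5%, -11.4).** Both sSOL tests succeed 82.8% of the time. All six succeed 69.0, 70.5 and 72.6% of the time for correlations of 0, 0.25 and 0.5, and about 76.5% at 0.8.

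**How far the 71% could move.** These inputs are assumptions; none is in the documents.
- Baseline adjustment on the raw scale, residual SD = 33 × √(1 − r²): a baseline-change correlation of 0.3, 0.5 or 0.6 gives SD 31.5, 28.6 or 26.4 and power 75.2, 82.9 or 88.3% at -6.8.
- Missing data: if 20% or 30% of subjects contributed nothing at Month 6 (240 or 210 per group), power at -6.8 falls to about 62% or 56%.

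**The case against.** Five points can be made for the plan.

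- **Table 4 already shows the shortfall.** It does list 371 and 496 per group at -6.8, and a careful reader can infer power below 80%. But it gives sample sizes, not power at 300. The text around it concludes that power is sufficient, and the Synopsis omits the table.
- **The arithmetic is right.** It is: the sSOL sentence is conditional on -8.7 and correct to rounding. What fails is the general claim built on it.
- **71% is not the power of the planned test.** This stands as a limit. The figure puts a difference in medians into an unadjusted raw-minute comparison, with an SD that SAP 2 says was taken across doses of 1 to 25 mg. The planned test is a baseline-adjusted MMRM on log(sSOL), and adjustment could take power above 80%. But the documents give no log-scale SD or baseline correlation, so they do not support the claim by that route either, and missing data pull the other way.
- **-6.8 is one noisy input.** The sSOL medians run against the dose order seen for sSE and sWASO, and the simple average of the two, -10.0, would give 96%. An intermediate target can be defended, but the plan has to say that this is what -8.7 is and why.
- **Sequence power needs assumed correlations.** This is true for all six tests, so the range must be labelled as assumed. The 71% limit through step e needs no such assumption.

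**Conclusion.** The concern holds. By the plan's own inputs and method, LEM10 on sSOL has about 71% power with 300 per group, not the roughly 90% that the power sentence conveys. Step a then fails about 29% of the time and closes the whole confirmatory sequence, although LEM5 on sSOL has 99.8% stand-alone power. At the plan's estimates the chance of passing all six tests is about 64 to 66% for assumed endpoint correlations of 0 to 0.5. The stated sSE and sWASO figures are stand-alone, despite the statement that sample size rested on the sequential procedure.

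This is a finding about the stated justification. It does not predict the power of the log-scale MMRM, which could be higher or lower and cannot be derived from the documents.

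**What to change.** In the Synopsis, Protocol 9.7.2 and SAP 2, replace the unqualified sufficiency sentence with text such as:

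> *With 300 per group, power for sSOL is about 90% at a detectable difference of -8.7 minutes, about 71% for LEM10 at -6.8 and 99.8% for LEM5 at -13.2. At the Study 201 estimates the chance of passing steps a to e is about 71%, and of passing all six about 64 to 66% (assumed endpoint correlation 0 to 0.5). The sSE and sWASO figures are stand-alone. All figures are for an unadjusted two-sample comparison in raw units, using median differences for sSOL, with no allowance for missing data. The log-scale, baseline-adjusted MMRM may have different power, which was not calculated.*

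Label -8.7 as the detectable difference, or give its source.

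The cost is a less favourable, qualified power statement in three places. The tests, their order, alpha and the number of patients do not change.

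### The 90% power quoted for sWASO is per-comparison power; at the plan's own sSOL target the gate-keeping sequence caps the chance of a confirmatory sWASO result at about 83%

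*Protocol*

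**What the plan says.** On the basis of the estimate, protocol 9.7.2 states: "This estimate was based on sequential gate-keeping procedure". The same sentence goes on to give the 0.05 alpha level and refers back to the earlier description of the procedure. The section then claims sufficient power for the primary and key secondary endpoints. For sWASO it says that 900 subjects, 300 per group, "will give 90% power to detect a difference of -11.4 minutes for LEM5 and LEM10 compared to PBO", and concludes that the study is adequately powered for both doses. The synopsis carries the same text. SAP 2 repeats it in the past tense: "gave 90% power to detect a difference of -11.4 minutes for LEM5 and LEM10 compared to PBO".

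The order of testing is in protocol 9.7.1.6 under Control of Type 1 Error: sSOL for LEM10 and LEM5 (steps a and b), sSE for LEM10 and LEM5 (c and d), and then sWASO. The fifth step reads "e. Change from Study Baseline at Month 6 in sWASO, LEM10 compared to PBO"; the sixth and last, step f, is the corresponding sWASO test for the lower dose.

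Each step must be significant at two-sided 0.05 before the next is tested. SAP 3.3.3 gives the same order and adds: "The key secondary endpoints will only be tested if both primary analyses are statistically significant at the 0.05 level". Neither document gives a probability of passing the sequence, or any part of it.

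**The concern.** The section names the gate-keeping procedure as the basis of the estimate and then gives 90% for the last endpoint in the sequence. A reader could take 90% as the chance that the trial delivers a confirmatory sleep-maintenance result for each dose. Under the testing rule, that result also needs four earlier tests to succeed, two of them on sSOL with about 90% power each. If the quoted figure leaves those steps out, the chance of a confirmatory sWASO finding is lower than the text suggests. No test becomes invalid and no error rate changes. What is at stake is how much confidence in the sleep-maintenance claim the plan can honestly state.

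**Working it through.** **Inputs.** From protocol 9.7.2: SD 33 minutes (sSOL), 12% (sSE) and 43 minutes (sWASO); target differences 8.7 minutes, 5.5% and 11.4 minutes; 300 per group. From 9.7.1.6: two-sided 0.05 at every step. From 9.4.3: allocation about 1:1:1, so the LEM10 and LEM5 contrasts on one endpoint share a placebo arm and correlate 0.5. The documents give no correlation between endpoints.

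**Step 1: reproduce the plan's figures.** Per-comparison power ≈ Φ(δ / (SD·√(2/n)) − 1.96), with √(2/300) = 0.08165.
- sWASO: SE = 43 × 0.08165 = 3.511; 11.4 / 3.511 = 3.247; Φ(1.287) = 90.1% (90.0% by noncentral t). The n for 90% power is 299, against 300 in Table 4.
- sSOL: SE = 33 × 0.08165 = 2.694; 8.7 / 2.694 = 3.229; Φ(1.269) = 89.8%. The plan says above 90%; the gap is trivial.
- sSE: SE = 12 × 0.08165 = 0.980; 5.5 / 0.980 = 5.613; Φ(3.653) = 99.99%.

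The sWASO figure therefore matches a single comparison at unadjusted two-sided 0.05. A one-sided 0.05 test would give 94.5% and a Bonferroni 0.025 would give 84.3%. No gate-keeping is in the number.

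**Step 2: the ceiling.** Steps e and f are reached only if a and b both succeed, so P(pass e) and P(pass f) are each at most P(a and b). For two normal statistics with mean 3.229, correlation 0.5 and critical value 1.96, P(a and b) = 82.9%. Adding the sSE steps leaves 82.9%, because they are passed almost surely. This bound needs no cross-endpoint correlation. Even a single sSOL test, at 89.8%, is already slightly below 90%.

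**Step 3: illustrative sequence figures.** Six-variate normal simulation, 2 million draws, correlation 0.5 between doses. The cross-endpoint correlation is an assumption, varied from 0 to 0.9.

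| Effects assumed | P(a and b) | Through step e | Through step f |
|---|---|---|---|
| Planning targets: sSOL -8.7, sSE 5.5, sWASO -11.4, both doses | 82.9% | 74.7–80.5% | 69.2–78.4% |
| sSOL -8.7 both doses; Study 201 sSE (9.5 for LEM10, 5.5 for LEM5) and sWASO (-26.6, -11.3) | 82.9% | 82.9% | 74–80% |
| sSOL -10 both doses (a Table 4 row); Study 201 sSE and sWASO | 92.9% | 92.9% | 83–87% |

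Nearly all of the variation at step e comes from the sSOL gates and the sWASO effect assumed for LEM10. The calculation treats sSOL in minutes and includes no dropout, as the plan's own does.

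**The case against.** The strongest reply is that the sentence on gate-keeping concerns alpha only. It continues to the 0.05 level, Table 4 is headed by that alpha, and fixed-sequence testing is exactly what lets every comparison use the full 0.05. The sSOL and sSE sentences also describe power for comparing one dose with placebo. Quoting marginal power under a fixed sequence is common practice. This stands to the extent that a reader might infer the 90% is miscalculated, or that the sentence is plainly untrue. The documents support neither: the 90% reproduces, and the wording is ambiguous rather than false. But nothing in the text says that the powers are marginal, and the claim of sufficient power for the key secondary endpoints follows directly.

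A second objection is that the sequence percentages are not firm, and this stands too. A reader might take 75–80% and 69–78% as the design's true power. They rest on an assumed cross-endpoint correlation and on -11.4 minutes for LEM10, although the same section reports -26.6 for that dose in Study 201. They also rest on minute-scale sSOL, whereas SAP 3 and 3.4.1 test log-transformed sSOL. A reader might go lower still by inserting the Study 201 sSOL differences (-6.8 and -13.2), which gives about 71% at step e and 64–67% at step f. But those are median differences, which the plan used because mean differences were not available. A larger sSOL effect moves the result the other way, as the -10 row shows.

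**Conclusion.** The concern holds as a matter of what the stated power means. The 90% is sound per-comparison power, but it is not the probability of a confirmatory sWASO result under the sequence that the plan specifies. At the plan's sSOL target that probability is at most about 83% for either dose, roughly 7 percentage points below the quoted figure (90 − 83). This bound rests only on the plan's sSOL inputs, 300 per group and the shared placebo arm. It does not depend on the cross-endpoint correlation.

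The figures below the ceiling are illustrations conditional on the assumptions above. A reader might also infer that the trial is too small or that its error control fails. The documents do not support either: the type 1 error procedure is unaffected, and the plan sets no target for power through the whole sequence.

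**What to change.** In protocol 9.7.2, the synopsis and SAP 2:
1. State that the sSOL, sSE and sWASO powers are per-comparison (marginal) at two-sided 0.05 and exclude the probability of passing earlier steps.
2. Add that, at the planning effects, the probability of reaching and passing step e or step f is at most about 83%.
3. Qualify accordingly the claim that the study is adequately powered on sWASO for both doses.
4. If sequence figures are given, show them as ranges with their assumptions. With cross-endpoint correlation 0 to 0.9 and sWASO -11.4 for both doses, they are about 75–80% at step e and 69–78% at step f. With Study 201 sSE and sWASO effects and sSOL at -8.7, they are about 83% and 74–80%. Note that sSOL is on the minute scale and that no dropout is included.

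The cost is text only, with no change to sample size, alpha or conduct. The stated position becomes less favourable.
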